Title Page

Protocol Title: Effects of bodily illusion and tDCS on SCI-related neuropathic pain

Protocol Number: 20200841 eProst ID number

Date: 2/21/24

Version 1.0

PI Name: [name]

NCT Number: NCT04578574

1) Protocol Title

Effects of bodily illusion and tDCS on SCI-related neuropathic pain

2) Objectives

Specific Aim #1: We aim to determine to what extent neuropathic pain following spinal cord injury (SCI) is reduced after a non-pharmacological treatment involving bodily illusion (BI) and transcranial Direct Current Stimulation (tDCS).

Specific Aim #2: We aim to determine the relationship between Body Representation (BR) and neuropathic pain after SCI by investigating BR measures (e.g. body image task) before and after the exposure to BI and tDCS. Electrophysiological (EEG) measures before and after exposure to BI and tDCS will be also investigated.

The working hypothesis is that a manipulation of the BR through a long exposure of BI and tDCS will reduce neuropathic pain symptom severity and sensory abnormalities. Moreover, this research will provide insights into changes of BR and EEG measures after SCI so far neglected, given the measures of EEG and body image task taken before and after BI-tDCS.

3) Background

Following SCI persistent neuropathic pain is a common clinical condition that negatively influences quality of life (QoL) and independent living of SCI individuals by interfering with sleep, mood, physical and social activities (*Wollaars et al., 2007*). Unfortunately, the neuropathic pains that occur after SCI are often inadequately relieved by available treatments, with pharmacological gold standard treatments reducing pain by 50% or more in only one person out of seven (*Cardenas et al., 2013*). Thus, interdisciplinary, multimodal treatment approaches are particularly important to consider in this population. Indeed, our recent qualitative research shows that a priority of many SCI individuals who experience severe neuropathic pain is to have better access to non-pharmacological treatment options.

Research shows that non-pharmacological intervention that synergistically modulates neural activity with the purpose of inducing changes in body representation (BR) decreases neuropathic pain (*Moseley, 2007; Soler et al., 2010*). In particular the combination of tDCS (a non-invasive brain stimulation able to modulate neural excitability, depending on the polarity of stimulation) and different types of bodily illusions (like, rubber hand illusions and walking illusion) to manipulate BR induce analgesic effects (*Soler et al., 2010*).

Body representation is a multidimensional concept requiring the integration and organization of multiple sensory inputs, such as somatosensory,

proprioceptive and kinesthetic coming from skin, joints and muscles with visual information (Carruthers, 2008; Deneve & Pouget, 2004; Longo *et al.*, 2010). Under normal circumstances these information are integrated to provide a coherent sense of one's own body (Longo *et al.*, 2010). BR can be manipulated by using non-invasive approaches that manipulates the interaction between vision, touch and proprioception, such as the rubber hand illusion (RHI) (Botvinick & Cohen, 1998; Tsakiris & Haggard, 2005) and walking illusion (WI) (Moseley, 2007; Soler *et al.*, 2010). In the RHI a prosthetic hand brushed synchronously with a participant's own hand is perceived being part of the participant's own body. Similarly in the WI a participant on a wheelchair can see his/her upper body on a mirror, while the lower part of the body is a projection on the screen of legs in motion. Both illusions are able to manipulate BR through vision and proprioceptive manipulations and reduce neuropathic pain.

In addition the use of tDCS over specific brain areas (e.g., motor cortex) in combination with bodily illusions has been used to treat neuropathic pain given the long lasting analgesic effect. Moreover, the modulations of embodiment processes for an artificial limb (e.g. RHI), such as the sense of body ownership, have been shown to be induced by tDCS over posterior parietal cortical (PPC) areas. There is therefore evidence that modulation of PPC can temporarily induce changes in body representation.

Finally, EEG research(Boord *et al.*, 2008; Vuckovic *et al.*, 2014) suggests that SCI-related neuropathic pain is associated with increased EEG power spectra in the theta range (4–7 Hz) and decreased power in alpha (8–13 Hz) and beta (13-20 Hz). These power spectra variations are attributed to altered inputs from the thalamus, a phenomenon known thalamocortical dysrhythmia. Brain rhythms can be modulated via non-invasive neuromodulatory interventions. For instance, tDCS induces neuronal membrane excitability that leads to changes in cortical activity. Anodal tDCS has been shown to modulate spontaneous oscillatory brain activity in the resting brain (e.g., an increase in alpha and beta power) after stimulation(Mangia *et al.*, 2014). In addition tDCS over posterior parietal cortical areas has been shown to modulate aspects of multisensory body representation and increase cortical response to incoming visuo-spatial stimuli(Grasso *et al.*, 2020; Spitoni *et al.*, 2013) important for body representation.

In this protocol we aim to stimulate PPC by using tDCS or sham (inactive t-DCS) and at the participants will undergo to bodily illusion (BI) sessions.

4) Study Design

Purpose: The study is a pilot study investigating to what extent neuropathic pain is reduced after BI-tDCS stimulation in participants with SCI and neuropathic pain. (See also objectives above)

Number of Participants: In this pilot study 16 participants with SCI and neuropathic pain will be enrolled.

Number of study arms: two study arms

Study model: Experimental arm (half participants will undergo BI-tDCS) and Sham comparator arm (half participants will undergo BI- inactive tDCS).

Inclusion and Exclusion Criteria

Inclusion criteria

SCI and chronic pain (SCICP) group (N=16): Participants will be men or women, 18-75 years of age, with an incomplete cervical traumatic SCI. Participants must have experienced neuropathic pain for a minimum of six months. They must have neuropathic pain in the moderate to severe category, which will be defined as a score of at least 4 on a NRS (range of 0 to 10). Participants must be willing and able to sign informed consent.

Exclusion criteria

General: Candidates will be excluded if they have: (1) major psychiatric disease/disorder (self-reported); (2) a significant neurological trauma besides SCI (3) a recent (one-year) history of alcohol or drug abuse (self-reported); (4) any other medical conditions in which transcranial DCS is relatively contraindicated, such as pregnancy, epilepsy and/or seizures.

Arms and Interventions

| Groups | Arms and Interventions | Intervention |
|---------------------------|------------------------|---------------------------------|
| Group 1 (8 SCI with Pain) | Experimental arm | BI-tDCS over 2-4 weeks |
| Group 2 (8 SCI with Pain) | Sham comparator arm | BI-inactive tDCS over 2-4 weeks |

Procedures Involved

Participants will complete Pain/Sensory examination, EEG recording at rest and BR measures before BI and tDCS exposure (or BI and inactive tDCS: sham) (PRE-Session 1), then they will undergo 10 study sessions of BI and tDCS (or sham), 30 min, during a period of 2-4 weeks (from Monday to Friday) (Sessions 2-11). Finally, they will complete Pain/Sensory examination, EEG recording at rest and BR measures after BI and tDCS exposure (or sham) (POST- Session 12). See details below.

| Session 1 - Baseline | Sessions 2-11 | Session 12 |
|--|---------------|--------------------------------|
| Screening: Information on Injury; Age; Sex; BMI, Inclusion/Exclusion criteria listed above | BI-tDCS | - |
| BR measures: Computer task: mental rotation of body parts | | BR measures |
| EEG recording at rest | | EEG recording at rest |
| Sensory and Pain Assessment: QST; NPSI; ISCPBDS; PGIC | | Sensory and Pain Assessment |
| Other Questionnaires: PGWBI; BDI; CDS, Illusion measure | | Other Questionnaires |

PRE-Session (1). This session is done in a single visit of a duration of three hours, however, if necessary, we will divide the tests in 2 visits over 1 week, to meet participants' need.

BR measures: A computer task (mental rotation of body parts) will be performed **PRE** and **POST** BI-tDCS (or BI and inactive tDCS:sham). The mental rotation of body parts is assumed to activate somatosensory representations, such as the body schema. In this task participants will be instructed to perform a computer task: the mental rotation task of body parts. They will observe images of hands or feet (left and right) on a computer screen or objects (left or right oriented) in different angle orientation and they will have to judge the laterality of the image (left or right). Reaction times will be measured and defined as a difference from image onset and participant's vocal response, accuracy (correct responses) will be also evaluated.

EEG recording at rest: A 64-channel Biosemi EEG-system will be used to record cortical activity under two conditions of 5 min each: while subjects will rest with their eyes closed (EC), and while they will rest with their eyes open (EO) keeping the gaze on a fixation cross in the middle of a computer screen. These measures will be performed at baseline (**PRE**) and directly after treatment completion (BI-tDCS or BI-sham) (**POST**). Absolute spectral power will be calculated in the frequency range of 4–35 Hz, as we will focus our analysis on theta (4–7 Hz), alpha (8–13 Hz), low beta (13–20 Hz) and high beta (20–30 Hz).

Questionnaires: First they will be requested to report their height and weight to calculate body mass index (BMI). Participants will be also asked to complete 4 questionnaires: the Neuropathic Pain Symptom Inventory (NPSI), psychological general well-being index (PGWBI) questionnaire, the Beck Depression Inventory-II (BDI-II) and the Cambridge Depersonalization Scale. We will also perform a pain assessment using the Pain Basic Data Set where participants will describe their pains and provide the Patients' Global Impression of Change (PGIC):

1. The psychological general well-being index, The PGWBI is a validated Health

Related Quality of Life (HRQoL) measure, widely used in clinical trials and epidemiological research to provide a general evaluation of self-perceived psychological health and well-being. Participants are required to indicate the answer that best applies to them, choosing one of the 6 options (Grossi et al., 2006). It is composed of 22 items, rated on a 6-point scale (0 to 5). The scores for all items can be summarized into a summary score, which reaches a maximum of 110 points, representing the best achievable level of well-being.

2. Beck Depression Inventory, 2nd Edition (BDI): The BDI is a self-report multiple choice questionnaire designed to assess depressive symptoms (Steer et al., 2001). Participants are required to rate their symptoms over the past two weeks from 0-3 with increasing scores reflecting greater symptomatology. It is composed of 21 items. Each item is rated on a 4-point scale ranging from 0 to 3. Range of depression: 0–13 minimal, 14–19 mild, 20–28 moderate, and 29–63 severe.

3. The Cambridge Depersonalization Scale is a well-validated scale designed to assess disturbance of the apparent reality of one's physical states, as well as, altered perception of bodily experience. Participants are required to indicate the Frequency (from 0 to 4) and the Duration (from 1 to 6) of the bodily experiences that they may have in their life (Sierra & Berrios, 2000). It is composed by 29 items. Each one of the 29 items is rated on two independent Likert scales, one for frequency and duration. A total score is calculated by adding all item scores. It has been established a score cut off of 70, >70 it is considered a depersonalization disorder.

4. Neuropathic Pain Symptom Inventory (NPSI): The NPSI (Bouhassira et al., 2005) assesses pain symptom severity associated with *neuropathic pain*. The NPSI is a 12 items questionnaire with a range of scores from 0 to 10 for all items, except for questions number 4 and 7 where the response is open. With a Total score maximum of 100 (summation of the 10 items except of item 4 and 7) indicating a clinically relevant dimension of neuropathic pain syndrome. The NPSI is also constituted of 5 subscales with a maximum total score of 10, indicating the specific dimensions of pain (burning, pressing, paroxysmal pain, evoked pain and paresthesia/dysesthesia). The NPSI includes severity ratings of *10 pain descriptors reflecting* spontaneous ongoing or paroxysmal pain, evoked pain (i.e. mechanical and thermal allodynia/hyperalgesia) and dysesthesia/ paresthesia. In addition, the NPSI includes two temporal items for duration of spontaneous ongoing pain and paroxysmal pain. The NPSI allows discrimination and quantification of five distinct and clinically relevant dimensions of neuropathic pain. The NPSI has been shown to be both valid and reliable in heterogeneous chronic pain populations.

5. International Spinal Cord Injury Pain Basic Data Set (ISCIPIBDS) The ISCIPIBDS is a brief instrument that contains questions about clinically relevant information concerning up to three separate pain problems during the last week including pain interference with sleep, activities, and mood, pain intensity, and pain classification (Widerström-Noga et al., 2014). Respondents are asked to rate the interference items on a 0 to 10 scale.

Patients' Global Impression of Change (PGIC): The PGIC scale was designed specifically to assess patients' perception of changes following treatment (i.e., "feeling better" or "feeling worse"). It is a 7-point verbal scale, with the options "very much improved" (3), "much improved" (2), "minimally improved" (0), "no change" (0), "minimally worsened" (-1) "much worsened" (-2), and "very much worsened" (-3). It has been demonstrated that the subjective "much improved" and "very much improved" ratings indicate moderately important and substantial improvement and the PGIC is widely used in neuropathic pain studies.

Sensory and Pain examination: All participants are required to have an AIS score. A trained examiner will conduct a standard neurological examination for SCI, including determination of the level of injury and classification on the American Spinal Injury Association (ASIA) Impairment Scale (AIS):

- *Quantitative sensory testing (QST) using Medoc machine (Medoc Ltd, Ramat Yishai, Israel and FDA approved)* The sensory assessment is intended to detect and quantify positive and negative sensory signs indicative of somatosensory (dys)function. A standardized QST protocol is commonly used in clinical and research settings to provide essential information regarding an individual's sensory status and has been used extensively in our research group (Widerström-Noga *et al.*, 2016). As part of the QST protocol, we will also assess mechanical and thermal allodynia. Ascending somatosensory information is transmitted mainly via the dorsal column-medial lemniscal (body) and the trigeminal lemniscus (face) for innocuous tactile and proprioceptive sensations, and via the spinothalamic tract (body) and the trigeminothalamic tract (face) for thermal and pain sensations. Somatosensory thresholds will be measured at two standard test sites in all subjects, the right cheek, near angle of nose and the thenar eminence, center. The right cheek will be chosen because this site is above the level of injury for all subjects.
- *Assessment of thermal allodynia:* An allodynic response is a painful response evoked by a stimulus that is not normally painful. We will use two thermorollers [Somedic, Sweden], one set at 40°C (corresponding to approximately 7 degrees above normal skin temperature), and the other at 25°C (approximately 8 degrees below normal skin temperature). Moving the rollers along the skin surface enables quick location of areas with abnormal temperature sensibility. If the subject perceives the thermal sensation as pain, it will be interpreted as thermal allodynia and the subject will be asked to rate the sensation on an NRS.
- *Assessment of dynamic and static mechanical allodynia:* Dynamic mechanical allodynia will be investigated similarly to the method described by (Cruz-Almeida *et al.*, 2012), who used a soft brush and lightly brushed the skin in the painful area. If pain is evoked in a test

site, the participant will be asked to rate the pain intensity by using an NRS. Static mechanical allodynia will be assessed using Semmes-Weinstein monofilaments. Evoked pain intensity will be rated on an NRS.

- Pain assessments:

Numerical Rating Scale (NRS): Numerical rating scales are widely accepted and used for the measurement of pain intensity. In this study, we will use this scale to assess the subjects' ratings of pain sensation on a scale of 0 (no pain) to 10 (most intense pain imaginable). For pain history, the International SCI Pain Basic Data Set (ISCIIPBDS, version 2.0) will be used.

Session 2-11) BI-tDCS

Participants will undergo 10 study sessions of BI and tDCS, 30 min, during a period of 2-4 weeks (from Monday to Friday) (Sessions 2-11). We will allow for up to 3 missed sessions.

BI procedure: Two types of illusions will be used 15 min each, the rubber hand illusion (RHI) and the walking illusion (WI) to target upper and lower limbs. In the RHI a prosthetic hand will rest inside a box in front of the subject's midline at the same distance in front of the subject's chest as the subject's hand is. The entire box will be covered by a mirror, which prevents the subject from seeing their hand. The procedure requires that participants will only see the rubber hand while stimulated (tactile stimulation by using a paintbrush) and at the same time their hand will be also stimulated but hidden from their view. This will create a visual illusion as the fake hand will be perceived as one's own hand. For the WI participants will sit in their wheelchair and a screen will be placed in front of them, composed by a half mirror (top part) and half projector-screen (bottom part). Participants will be instructed to move their upper body and observe themselves in the mirror, while online a video of a walking person will be projected on the half bottom part of the screen. This will give the illusion of walking. After each illusion we will ask participants questions about the strength of the illusion. We will use the body ownership subscale (5 items) of the 27 items that compose the psychometric perspective of the embodiment after bodily illusion by Longo et al. in 2008 (*Longo et al., 2008*). The 5 items of the questionnaire include questions about the feeling of body ownership of the rubber hand and virtual legs, the response options range from -3 (completely disagree) to +3 (completely agree).

tDCS: Direct current will be delivered from a battery-driven, constant current stimulator (TCT Research Version, Hong Kong) using saline-soaked surface sponge electrodes (35 cm²). The anode will be placed over P4 (EEG 10/20 system) to target the right Posterior Parietal Cortex (rPPC), and the cathode over the contralateral supraorbital area. This electrode position is chosen because rPPC has been shown to be involved in

multisensory integration, BR and localization of somatic stimuli (*Azañón et al., 2010; De Vignemont, 2007; Makin et al., 2008; Wertheim et al., 2020*). However, consistent with other tDCS studies on pain (*Soler et al., 2010*), where the site of stimulation is contralateral to the painful body-part, if participants have not bilateral pain and the painful site involves only the right side of the body, the anodal electrode will be placed on P3, the left Posterior Parietal cortex (lPPC), and be therefore contralateral to the painful body-part. A constant current of 2mA intensity will be applied for 30 min during the BI (15 min RHI plus 15 min WI). The duration of the stimulation has been chosen as used in previous works (*Mameli et al., 2014; Ouellet et al., 2015*).

In the sham session (inactive tDCS) there will be no stimulation. The procedure will be the same as the active tDCS but the machine will be turned off after 30 seconds.

tDCS it is not a medical device and it is considered a non-significant-risk device, meaning that it is a technique without expectation of any Serious Adverse Effect (*Bikson et al., 2016; Fregni et al., 2015*).

In the United States tDCS is not FDA approved. Some companies have an FDA (Food and Drug Administration) regulation status of “investigational” which limits the device to investigational use and not for medical treatment (*Fregni et al., 2015*). In the European Union, Canada, Brazil, Australia, and Singapore, specific tDCS products have been approved for treatment of various neuropsychiatric disorders. (*Fregni et al., 2015*).

Research centers worldwide are allowed to test tDCS in controlled clinical trials. A list of tDCS trials can be found here: clinicaltrials.gov

POST- Session (12)

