Risks/discomforts associated with measurement of sensory function (QST): Pain thresholds will be measured for cold and hot temperatures. Each stimulus trial will start at a neutral temperature (32 °C) and will be increased (for hot pain) until the participant indicates that the stimulus has just become painful. This will result in slight discomfort for the participant. As soon as the participant tells the experimenter that the stimulus is painful, the stimulus will immediately be terminated. Cut-off temperatures are in place (50 °C for hot pain) so that no extreme temperatures will be presented. The cut-off value is well below temperatures at which any skin damage would result. The equipment used for sensory testing has been used in our laboratory for many years, without any adverse events. This equipment is also used in many other laboratories and has an excellent track record.

Risks/discomforts associated with BI: bodily illusions are commonly used research tools with no risk for participants.

Risks/discomforts associated with EEG measures: EEG records brain activity at no risk to participants. The EEG is used with the only purpose of recording, the electrodes are placed on the scalp attached to a custom cap with prepared holes. We use an EEG system with active electrodes (Biosemi Active Two 64 channels: https://www.biosemi.com/faq/skin_preparation.htm) and so high electrode impedance are tolerated, and the system can be used without the usual skin preparation (scrubbing) to lower impedance. This minimizes discomfort and eliminates risks of infection. In the case of electrodes placed around the face, it is possible that participants with very sensitive skin may experience redness, however this will be very minor and solve within minutes. We use a low impedance highly conductive saline gel (Signa gel by Parker), formulated to maximize contact between the body surface and the Active electrodes, bacteriostatic, non-irritating, and non-staining.

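### Bodily illusions are said to carry no risk, yet the rubber hand illusion brushes an unspecified hand that may be allodynic or have reduced sensation, and pain from brushing is not captured

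*Combined protocol and SAP*

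**What the plan says.** **The intervention.** Section 4, BI procedure, gives each session 15 minutes of RHI and 15 minutes of walking illusion. In the RHI the participant watches a rubber hand being stroked ("tactile stimulation by using a paintbrush) and at the same time their hand will be also stimulated but hidden from their view"). Ten sessions are planned and up to three may be missed. The text does not say which hand is brushed and refers to no Session 1 finding. It states the result without condition: "This will create a visual illusion as the fake hand will be perceived as one's own hand".

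**The population.** The inclusion criteria require participants to be "18-75 years of age, with an incomplete cervical traumatic SCI", with neuropathic pain for at least six months, rated at least 4 on the NRS. No criterion concerns sensation or allodynia in the hand.

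**The sensory examination.** Session 1 measures thresholds at the right cheek and at the thenar eminence (side not stated). Only the cheek is said to lie above the injury in everyone. Dynamic allodynia is tested by a published method that "used a soft brush and lightly brushed the skin in the painful area. If pain is evoked in a test" site, its intensity is rated on the NRS.

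**The risk text.** Under Risks to Subjects, the entry for BI says "bodily illusions are commonly used research tools with no risk for participants". The adverse-event list is headed as relating to electrical stimulation. The sentences on reporting side effects, and on stopping because of discomfort, follow from that list.

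**The concern.** A paintbrush on the hand is close in kind to the soft brush used to test for dynamic allodynia. A cervical injury can affect the hand, and everyone enrolled has neuropathic pain. Two kinds of participant follow. In one, the brushed hand is allodynic and the intervention itself may hurt. In the other, sensation in the brushed hand is reduced and the illusion may be weaker.

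The plan identifies neither before Session 2. It has no defined place to record pain from brushing, and it describes the illusions as free of risk. The outcome is also touched: the NPSI total, the tentative primary measure, includes evoked pain, and section 4 defines that to include mechanical allodynia. Repeated brushing of an allodynic hand therefore bears on items that the outcome scores.

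**Working it through.** The plan gives no figure on this point, so there is none to reproduce. The check compares passages and then gauges scale.

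**1. Do the passages fit together?** The allodynia test accepts that light brushing of painful skin may evoke pain. The RHI applies brushing to a hand that no sentence restricts to non-painful skin. The BI risk entry allows no exception. All three can be true only if no participant's brushed hand is allodynic, and nothing in the plan ensures that. The plan does adapt the tDCS anode side to the painful side (P4, or P3 when pain is only on the right), but has no matching statement for the brushed hand.

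**2. Exposure.** RHI: 15 × 10 = 150 min. All BI: 30 × 10 = 300 min. Share: 150/300 = 50%. With three missed sessions: 15 × 7 = 105 of 30 × 7 = 210 min, again 50%.

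**3. Effect on the arm comparison.** Both arms receive the same BI and only tDCS differs. Let p be the share affected and δ the shift that brushing causes in an affected participant's outcome.
- Expected shift: pδ in each arm, which cancels in the difference if δ is the same in both.
- Added within-arm variance: p(1 − p)δ², if δ is constant and unrelated to other variation. That is 0.09δ² at p = 10%, 0.21δ² at 30% and 0.25δ² at 50%.
- Dilution: any part of the tDCS effect that needs a working RHI is multiplied by (1 − p) if failure is all-or-none: 0.90, 0.70 and 0.50 at the same values. Partial failure dilutes less.
- Chance imbalance: each participant is 1/8 = 12.5% of an arm. If one arm has two more affected participants, the arm means differ by (2/8)δ = 0.25δ.

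**4. How likely is it?** The documents give no value for p, so the range is assumed. With 16 participants (8 per arm, section 4):
- P(at least one) = 1 − (1 − p)^16.
- P(arms differ by two or more) = sum of P(X = i)P(Y = j) over |i − j| ≥ 2, with X and Y independent Binomial(8, p).

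| p (assumed) | Expected of 16 | At least one | Arms differ by ≥ 2 |
|---|---|---|---|
| 10% | 1.6 | 0.815 | 0.192 |
| 20% | 3.2 | 0.972 | 0.339 |
| 30% | 4.8 | 0.997 | 0.411 |
| 50% | 8.0 | >0.999 | 0.454 |

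Section 14 gives a total of 20 instead of 16. On that figure the probability of at least one is 0.878 at p = 10% and 0.988 at 20%, so the reading does not change.

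**The case against.** The strongest reply is that little here is certain. Injuries are incomplete, so hand sensation may be preserved. Allodynia is not an entry criterion. The brush test is diagnostic, confined to painful skin and conditional in its wording. All of that stands: the conflict exists only where the brushed hand is allodynic, and the share is unknown.

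A reader might infer four stronger points that the documents do not support.

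- *The illusion cannot work unless the brush is felt.* Background does describe synchronous brushing ("In the RHI a prosthetic hand brushed synchronously with a participant's own hand is perceived being part of the participant's own body") and lists touch among the inputs. But its summary credits both illusions to vision and proprioception, and the BI procedure calls the RHI a visual illusion. That it may be weaker is a fair inference; that it must fail is not. The walking illusion, half of BI time, uses no brushing.
- *A null result could not be told apart from an illusion that was never induced.* Five ownership items, scored −3 to +3, are asked after each illusion, so a weak illusion would show. What is missing is a stated use for the score. Moreover, with no arm without BI, the arm comparison cannot isolate the effect of the illusions in any case.
- *The arm comparison is biased.* BI is common to both arms, so no systematic bias is expected.
- *Participants are told that there is no risk.* The statement is in the protocol's risk section. Consent pages are not among the material available, so what participants are told cannot be judged.

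One could also say that the promise to record any reported side effect covers brushing. In context it refers to the effects listed for electrical stimulation, so it is not a clear instruction.

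**Conclusion.** The point holds in a limited form and should be corrected. The unqualified no-risk statement does not sit with the protocol's own allodynia test, given brushing of an unspecified hand for 105 to 150 minutes in total among people with incomplete cervical injury and neuropathic pain. Pain from brushing has no defined route into the record.

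For the statistics, the expected consequence is dilution, added variance and possible chance imbalance at 8 per arm. Across an assumed share of 10% to 50%, at least one affected participant among 16 is likely (0.81 or more), and a difference of two or more between arms has probability 0.19 to 0.45. This rests on three assumptions: the share itself, participants being affected independently, and allocation being unrelated to the state of the hand. Cancellation of the mean shift also needs brushing to act alike in both arms. None of this invalidates the pilot.

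**What to change.** - Reconcile the BI risk entry under Risks to Subjects with the allodynia assessment and the BI procedure in section 4.
- Extend side-effect recording explicitly to pain evoked by brushing.
- At Session 1, record for each hand whether the brush is felt and whether it evokes pain. This is a small new item: the existing tests cover a thenar site of unstated side and brushing of the painful area only.
- Record which hand is brushed.
- Name the existing 5-item ownership score (mean over sessions, by arm) as the manipulation check when pain and reaction-time results are interpreted. Use it descriptively: Background says that parietal tDCS can itself change ownership, so it is not a neutral baseline covariate.

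Which hand to brush, and how to manage a participant for whom brushing is painful, are for the investigators to decide and write down.

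The cost is a minute or two at Session 1, a few lines of text and a less favourable risk statement. No extra visit or equipment is needed.
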